### *Withdrawal criteria and dropouts*

The patient can at any time decide to discontinue his/hers participation in the trial. In case of major serious per- or postoperative complications/events, the investigator can decide to withdraw the patient from the trial for the sake of the patient.

The number of dropouts and withdrawals will be reported in the final manuscript and new participants will be included until 2 x 270 patients have completed the trial. In order to complete the protocol the patient must have received the intervention/placebo and have a minimum of two postoperative cTnI assessments done within the first 4 postoperative days (the primary outcome). If the primary outcome is missing the short- and long-term follow-up will still be done and the patient will be included in the final analysis (intention-to-treat analysis). The patient will dropout if reoperated within the first 4 postoperative days.

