- Number of patients with peak plasma cardiac troponin I (cTnI)  $\geq$  45ng/L (99th percentile URL, 10% CV at 40ng/L) during surgery or during the first 4 days after surgery (perioperative myocardial injury). If elevated at baseline (preoperative) a 20% or greater increase of cTnI according to baseline is required for the diagnosis of a perioperative myocardial injury [15].
  - o Holstebro Hospital: Number of patients with peak plasma cardiac troponin I (cTnI) > 24 ng/L (99th percentile URL, 14% CV)

*Secondary outcome*

- Peak plasma cTnI and total cTnI release (area under the curve) during surgery or during the first 4 days after surgery
- Plasma N-terminal Pro-Brain Natriuretic Peptide (NT-proBNP) before surgery and at day 1 after surgery.
- Endothelial dysfunction assessed by the non-invasive EndoPat system (24 hours after surgery, only done at Zealand University Hospital)
- Biomarkers of coagulation (only patients included at Holstebro Hospital)
- Perioperative myocardial infarction (Universal definition of myocardial infarction, published in 2012 [15])
  - A typical rise or fall of cTnI with peak plasma cTnI  $\geq$  45ng/L (99th percentile URL, 10% CV at 40 ng/L) (Holstebro cTnI > 24 ng/L), and with at least one of the following:
    - Symptoms of ischemia

---

 Defined as a preoperative cTnI  $\geq$  45ng/L (99th percentile URL, 10% CV at 40ng/L)

- New or presumed new significant ST-segment-T wave (ST-T) changes or new left bundle branch block (LBBB)
  - Development of pathologic Q waves in the ECG
  - Imaging evidence of new loss of viable myocardium or new regional wall motion abnormality
  - Identification of an intracoronary thrombus by angiography or autopsy
- Cardiac death with symptoms suggestive of myocardial ischemia and presumed new ischemic ECG changes or new LBBB, but death occurred before cardiac biomarkers were obtained, or before cardiac biomarker values would be increased.
  - Development of new pathologic Q waves on an ECG or pathological findings of a healing myocardial infarction if troponin levels were obtained at times that could have missed the clinical event
- Major adverse cardiovascular events (30 days, one year and five years after surgery)

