#### *Participant timeline*

*Intervention:* The remote ischemic preconditioning procedure is carried out immediately after the induction of regional or general anesthesia. The blood pressure cuff is placed on the upper limb. The cuff is inflated to 200 mmHg resulting in a total occlusion of the blood flow to the limb. After 5 minutes of ischemia the cuff is deflated and the limb is reperfused for 5 minutes. The procedure is carried out 4 times in a row. For patients with systolic blood pressures >185 mmHg, the cuff will be inflated to at least 15 mmHg above the patient's systolic blood pressure. The first round should be completed before the initiation of surgery.

The patients will have blood collected to assess cTnI (preoperative and in the morning at days 1, 2, 3 and 4 after surgery) and NT proBNP (preoperative and in the morning at day 1 after surgery). All patients with a cTnI assessment  $\geq 45\text{ng/L}$  will have a minimum of one ECG performed and a medical doctor will evaluate the patient for the presence of an ischemic or non-ischemic event that can explain the elevated cTnI (i.e. sepsis, pulmonary embolism, cardioversion). The medical doctor will determine whether further action should be taken. If necessary, a cardiologist will be consulted. Patient included at Holstebro Hospital will have blood collected for assessment of coagulation biomarkers. The blood samples are taken preoperatively, 2 hours after incision and in the morning at day 1 and 2 after surgery (4 times 6 ml blood).

The investigator observes the patients during their stay in hospital and records the occurrence of any primary or secondary outcomes. The investigator will undertake a short- and long-term follow up (30 days, one and five years after surgery) and record the occurrence of any primary or secondary outcomes. The follow-up will be carried out by reviewing the patients' electronic hospital records, by a personal phone call and with data from the Danish National Patient Register and "Dødsårsagsregisteret".

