**The PIXIE study**

**Statistical analysis plan for the primary publication**

**Definitions of the population**

*Intention-to-treat:* randomized in the trial and a minimum of two postoperative troponin assessments within four days of surgery (an evaluable primary outcome)

*Per-protocol:* randomized in the trial, received the allocated treatment, and a minimum of two postoperative troponin assessments within four days of surgery

We will do a per-protocol analysis and an intention-to-treat analysis.

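### The final SAP's intention-to-treat set requires two postoperative troponins, so a patient whose only postoperative sample already establishes myocardial injury is in neither analysis set

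*Combined protocol and SAP*

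**What the plan says.** **Outcome definition (current protocol, Primary outcome).** The endpoint is the "Number of patients with peak plasma cardiac troponin I (cTnI") at or above 45 ng/L, or above 24 ng/L at Holstebro, "during surgery or during the first 4 days after surgery (perioperative myocardial injury"). If the preoperative value was already elevated, "a 20% or greater increase of cTnI according to baseline is required for the diagnosis of a perioperative myocardial injury". No confirmatory sample is asked for.

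**Sampling (current protocol, Participant timeline).** Troponin is drawn "preoperative and in the morning at days 1, 2, 3 and 4 after surgery".

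**Completion and replacement (current protocol, Withdrawal criteria and dropouts).** To complete the protocol a patient needs "a minimum of two postoperative cTnI assessments done within the first 4 postoperative days (the primary outcome"). Recruitment is open-ended: "new participants will be included until 2 x 270 patients have completed the trial". If the primary outcome is missing, follow-up continues and "the patient will be included in the final analysis (intention-to-treat analysis").

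**Analysis sets (final SAP, Definitions of the population; unchanged from the original SAP).** ITT means randomised with "a minimum of two postoperative troponin assessments within four days of surgery (an evaluable primary outcome"). The per-protocol set has the same sampling condition and also requires receipt of the allocated treatment.

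**The concern.** Two samples are a sensible minimum for calling a patient negative, because a single early negative can miss a later rise. They are not needed to call a patient positive: a later sample cannot lower a peak that has already crossed the threshold. The SAP applies the minimum to both.

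Take a patient with a normal preoperative value and a day 1 troponin of 300 ng/L who dies, withdraws or leaves hospital before the day 2 draw. The primary event has been observed, but the SAP calls the outcome not evaluable and leaves the patient out of the ITT comparison.

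The reasons for having only one sample may be linked to outcome. Staff and patients are not blinded, and the investigator may withdraw patients after major complications. If such losses differ between arms, the comparison among patients with two samples is no longer the randomised one. Recruiting further patients restores the number of completers, but neither the missing events nor the balance.

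**Working it through.** **1. The plan's own figure.** For 15% versus 7%, two-sided 5% and 80% power, the continuity-corrected two-proportion formula gives 264 per arm, as stated (239 without the correction). At 270 per arm the expected events are 270 × 0.15 = 40.5 and 270 × 0.07 = 18.9, together 59.4. Power of the uncorrected test is 84.6%. The sample size is not in dispute.

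**2. The rules for a patient with one postoperative sample.**

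| | First value qualifies | First value does not qualify |
|---|---|---|
| Primary outcome definition | Event established | Not yet known |
| Protocol, dropouts section | Not a completer; if the outcome counts as missing, kept in ITT, coding unstated | Same |
| Final SAP, ITT | Excluded | Excluded |
| Final SAP, per-protocol | Excluded | Excluded |

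The 20% rule does not change this, since one postoperative value and the preoperative value are enough to apply it.

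**3. Possible size (assumed inputs).** Let p be the true rate, f the share of randomised patients with exactly one sample, and q the share of those already qualifying. Assume one-sample patients who have not qualified stay event-free. With 270 two-sample patients per arm:

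- randomised per arm: N = 270/(1 − f)
- events outside the SAP sets: N × f × q
- rate in the SAP ITT set: (p − fq)/(1 − f)

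q is given for control and scaled by 7/15 for intervention. The last column counts all N patients at 15% and 7%.

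| f | q | Events outside (control / intervention) | SAP ITT rates | Power, SAP set | Power, all counted |
|---|---|---|---|---|---|
| 2% | 15% | 0.8 / 0.4 | 15.0% / 7.0% | 84.6% | 85.3% |
| 2% | 30% | 1.7 / 0.8 | 14.7% / 6.9% | 83.8% | 85.3% |
| 5% | 30% | 4.3 / 2.0 | 14.2% / 6.6% | 82.4% | 86.4% |
| 5% | 50% | 7.1 / 3.3 | 13.2% / 6.1% | 79.0% | 86.4% |
| 10% | 50% | 15.0 / 7.0 | 11.1% / 5.2% | 71.2% | 88.1% |

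Example, row 4: N = 270/0.95 = 284.2; 284.2 × 0.05 × 0.50 = 7.1; (0.15 − 0.025)/0.95 = 13.2%. The 10% row is a stress case.

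**4. Unequal loss, no true effect (15% in both arms).** With f = 1% versus 4%, the two-sided 5% test rejects 5.0% of the time at q = 15%, 5.3% at q = 30%, 6.6% at q = 50% and 7.7% at q = 60%. With f = 2% versus 10% and q = 50%, a stress case, it rejects 19.8%.

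**5. Leverage of one event.** By uncorrected chi-square, 40/270 versus 25/270 gives p = 0.047, and 40/270 versus 26/270 gives p = 0.066.

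**6. The simple remedy.** Suppose one-sample patients were admitted only when positive. The ITT rate would be p/(1 − f(1 − q)). With p = q = 15% and f = 4% this is 0.15/(1 − 0.04 × 0.85) = 15.5%, while the SAP rule gives 15.0%. For small f the errors are about f(q − p) under the SAP rule (q above p) and pf(1 − q) under this remedy. They are equal at q = 2p/(1 + p) = 0.30/1.15 = 26%. Below that, the remedy has the larger error.

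**The case against.** Four points can be made for the plan.

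**The protocol keeps these patients.** A reader might infer that the protocol itself discards and replaces observed events. It does not say so. Its dropouts section retains patients with a missing primary outcome in the ITT analysis, and the SAP's Sample size section describes the 2 × 270 target as per-protocol, so replacement only fills that target. This stands. The exclusion is explicit only in the SAP; in the protocol the gap is the missing coding rule.

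**Bias is not established.** A reader might also infer that incidence is understated in both arms, or that the most severe early events are removed selectively. The first holds only if one-sample patients qualify more often than patients overall (q above p); at q = p the rate is unchanged. The second needs to know why samples are missing, and a missed draw or ordinary discharge is as possible as early death. The rule is the same in both arms. The documents give no figures on any of this, so neither inference is supported.

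**A one-line exception would bring its own bias.** Admitting one-sample patients only when positive makes inclusion depend on the outcome (step 6). This stands and shapes the fix.

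**It is part of a wider problem.** Making ITT membership depend on troponin availability also excludes patients with no sample or one negative sample. That is so, and redefining ITT deals with all of them. The one-sample positive still needs naming, because there the outcome is known and no imputation is required.

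**Conclusion.** The point holds against the final SAP. Its ITT and per-protocol sets both leave out randomised patients whose single postoperative troponin already meets the primary outcome definition, and its ITT definition conflicts with the protocol's. This is a faulty rule rather than a missing detail.

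The size and direction of the effect are unknown. On assumed values of 2–5% one-sample patients, 30–50% of them positive in control, about 2–7 control and 1–3 intervention events would be left out. The effect on the estimated rates is nil if these patients qualify at the overall rate. Distortion of the type I error needs loss that differs by arm as well as q different from p, and is modest for differences such as 1% versus 4%. With only about 59 events expected, a borderline result could still turn on one or two of them. The change is worth making before the data are analysed.

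**What to change.** Reconcile the SAP's Definitions of the population with the protocol's dropouts section:

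- Define ITT as all randomised patients, whatever the number of samples.
- Count as an event any postoperative troponin within four days that meets the primary outcome definition (site cut-off, and the 20% rise if elevated at baseline).
- Apply the two-sample minimum only to classifying a patient as event-free.
- Treat patients with fewer than two samples and no qualifying value as having a missing outcome. Keep them in ITT under a prespecified method, such as multiple imputation using arm, site and the troponin values already seen, with best- and worst-case bounds. One-sample patients then do not enter only when positive.
- Report one-sample patients, and events among them, by arm.
- Keep the present two-sample set as a sensitivity analysis.

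The cost is a few sentences in the protocol and SAP, an explicit assumption about missing outcomes, and a little more analysis work. No new data, patients or sample-size change are needed.

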### *Data*

Data will be collected according to “Datatilsynet” and “Persondataloven”. The trial will be approved by the regional ethics committee, and the trial will be registered on [www.clinicaltrials.gov](http://www.clinicaltrials.gov) before inclusion of the first patient. All collected data will be registered in case report forms (CRFs) according to a list of source data. We will use paper CRFs, and later all data will be entered into an electronic database for statistical analysis. Electronic data will according to the approval by “Datatilsynet” be stored at an access limited drive.

### *Statistics*

All statistical analysis will be done with SPSS/PC+ package (SSPS, Chicago, IL, USA) or the SAS 9.3 package. Data will be analyzed using non-parametric or parametric statistics depending on the distribution of data. Differences are considered significant when  $p < 0.05$ . We will do a per-protocol analysis and an intention-to-treat analysis.

A medical doctor will evaluate all patients with a rise in cTnI  $\geq 45\text{ng/L}$  in order to determine whether the elevation in cTnI is due to an ischemic or non-ischemic disease. In the final data analysis, we will do an analysis, which includes all patients (ischemic and non-ischemic) and a second analysis, which will only include patients with an ischemic disease.

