#### *Allocation and blinding*

An electronic generator will create the randomization list.

Each patient allocation is randomly selected using sealed opaque envelopes. It is not possible to blind the staff or the patient. Assessor blinding will be performed and the unblinding will take place after final data analysis has been made. An independent data analysis team consisting of a statistician and an external medical scientist will perform interim analysis.

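### Holstebro troponin peaks above 24 and below 45 ng/L count as primary events but have no required ischaemic classification, and infarction may be incompletely ascertained in that range

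*Combined protocol and SAP*

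**What the plan says.** All references are to the current (multi-site) protocol and the final SAP.

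- **Outcome thresholds.** Under Primary outcome, the general rule is a peak of at least 45 ng/L, with one site exception: "Holstebro Hospital: Number of patients with peak plasma cardiac troponin I (cTnI) > 24 ng/L". The infarction definition under Secondary outcome carries the same exception: "Holstebro cTnI > 24 ng/L), and with at least one of the following". The section on plasma cardiac troponin I gives Holstebro an Abbott high-sensitive assay and the other two sites a Siemens one.
- **Work-up.** Participant timeline: "All patients with a cTnI assessment $\geq 45\text{ng/L}$ will have a minimum of one ECG performed". A doctor's evaluation for an ischaemic or non-ischaemic explanation follows from the same trigger. No Holstebro value is given.
- **Classification.** Statistics: "A medical doctor will evaluate all patients with a rise in cTnI $\geq 45\text{ng/L}$ in order to determine whether" the cause is ischaemic. Again no Holstebro value is given. The same section plans one analysis of all patients and "a second analysis, which will only include patients with an ischemic disease".
- **Other recording.** Participant timeline also says: "The investigator observes the patients during their stay in hospital and records the occurrence of any primary or secondary outcomes".
- **Blinding.** Allocation and blinding says of treatment: "It is not possible to blind the staff or the patient"; and of assessment: "Assessor blinding will be performed and the unblinding will take place after final data analysis has been made". It does not say what is assessed or by whom.
- **Final SAP.** The primary analysis is a chi-square test on the incidence of myocardial injury. Perioperative infarction is one of seven secondary comparisons. The ischaemic-only analysis is not listed.

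**The concern.** The outcome definitions were adapted to the Holstebro assay, but the steps that depend on them were not. A Holstebro patient whose peak lies above 24 and below 45 ng/L counts as having myocardial injury and reaches the troponin level for infarction. Nothing in the protocol requires that patient to have an ECG, a doctor's evaluation or an ischaemic/non-ischaemic label.

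Two results are touched. The protocol's second analysis needs a label that some primary events need never receive. The infarction comparison relies on five supporting criteria, two of which (ST-T change or new bundle branch block, and Q waves) can only be met with an ECG. Outside the 45 ng/L rule no ECG is scheduled; the ECG section says only who records it.

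A related gap concerns all sites. Restricting the second analysis to patients with ischaemic disease, read literally, leaves only cases. There would be no denominator by arm and so no incidence to compare. The SAP does not define the analysis either.

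**Working it through.** **1. Thresholds side by side**

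| Step | Siemens sites | Holstebro |
|---|---|---|
| Myocardial injury (Primary outcome) | ≥ 45 ng/L | > 24 ng/L |
| Troponin limb of infarction (Secondary outcome) | ≥ 45 ng/L | > 24 ng/L |
| Elevated baseline (footnote) | ≥ 45 ng/L | no separate value |
| ECG and doctor's evaluation (Participant timeline) | ≥ 45 ng/L | no separate value |
| Ischaemic classification (Statistics) | ≥ 45 ng/L | no separate value |

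The first two rows differ by site; the last three do not. Neither summary of changes nor the final SAP closes the gap. The single-site Køge protocol used 45 ng/L throughout, so this looks like an incomplete amendment rather than a choice.

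**2. Planned events**

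Inputs from the Sample size section: 15% versus 7%, two-sided 5%, power 80%, 270 per arm for evaluation. The plan's 264 per arm reproduces with a continuity correction:

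- n′ = [1.96√(2·0.11·0.89) + 0.8416√(0.15·0.85 + 0.07·0.93)]² / 0.08² = 239
- n = (n′/4)[1 + √(1 + 4/(0.08 n′))]² = 264

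Planned injury events: 270·0.15 + 270·0.07 = 40.5 + 18.9 = 59.4.

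**3. Events between the thresholds (illustration only)**

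The documents give neither Holstebro's share of events nor the share of its peaks between 24 and 45 ng/L. I assume 10–40% and 20–60%.

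- Fraction between thresholds, f: 0.10·0.20 = 0.02 to 0.40·0.60 = 0.24
- Events: 59.4·0.02 = 1.2 to 59.4·0.24 = 14.3

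**4. Second analysis**

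Suppose all other events are ischaemic and the unclassified ones are counted as non-events equally in both arms. Power by normal approximation, without continuity correction, is Φ{[d − 1.96√(2p̄q̄/270)] / √[(p₁q₁ + p₂q₂)/270]}, with q = 1 − p.

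- f = 0 (15% v 7%): 0.846
- f = 0.02 (14.7% v 6.86%): 0.838
- f = 0.24 (11.4% v 5.32%): 0.724

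**5. Infarction, if none between the thresholds is recorded in either arm**

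Assume a share m of injury events, 20% or 50%, meets the infarction criteria, the same above and below 45 ng/L. Total infarctions: 59.4·0.2 = 11.9 or 59.4·0.5 = 29.7. Between the thresholds: 11.9·0.02 = 0.24 to 29.7·0.24 = 7.1. The absolute difference is 8·m·(1 − f) points.

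| m | f | Difference (points) | Risk ratio | Power, 270 per arm |
|---|---|---|---|---|
| 0.2 | 0 | 1.60 | 0.467 | 0.24 |
| 0.2 | 0.02 | 1.57 | 0.467 | 0.24 |
| 0.2 | 0.24 | 1.22 | 0.467 | 0.195 |
| 0.5 | 0 | 4.00 | 0.467 | 0.53 |
| 0.5 | 0.02 | 3.92 | 0.467 | 0.52 |
| 0.5 | 0.24 | 3.04 | 0.467 | 0.42 |

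The risk ratio stays at 7/15 because both arms shrink by the same factor.

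**6. Infarction, unequal work-up and no true effect**

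Injury is 59.4/540 = 11% in each arm. Infarctions between the thresholds per arm: 270·0.11·f·m = 0.12 (f = 0.02, m = 0.2) to 3.56 (f = 0.24, m = 0.5). If all are found in one arm and none in the other, the false difference is 0.12/270 = 0.04 to 3.56/270 = 1.3 points. If 75% are found in one and 25% in the other, it is half that: 0.02 to 0.66 points.

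**Limit.** Steps 5 and 6 treat infarction as a fraction of injury. The definitions do not nest exactly: infarction allows a rise or a fall, while injury with an elevated baseline needs an increase of at least 20%.

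**The case against.** The main chi-square test needs only the troponin value, so a reader who infers that the primary result is compromised goes too far: this mismatch does not touch it. The ischaemic-only analysis is absent from the SAP for the primary publication, which leaves one secondary comparison out of seven. That comparison is underpowered under every assumption in the table, with or without the defect. All of this stands and limits the weight of the point.

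A reader might also infer that Holstebro infarctions in this range are bound to be missed. The documents do not support that. The investigator is to record any primary or secondary outcome in hospital, and symptoms, imaging, angiography and autopsy can satisfy the definition without a protocol ECG.

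Nor do they show bias between arms. Unblinded staff and discretionary work-up mean that a difference cannot be excluded, but unblinded staff may also carry out the work-up at 45 ng/L and above, and assessor blinding is planned. Blinded assessment cannot, however, recover an ECG that was never taken.

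Finally, every magnitude rests on assumed shares. That is correct: the low end is negligible, and the high end needs all the upper assumptions at once. None of these arguments removes the contradiction in the text.

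**Conclusion.** The point holds in a limited form. The protocol counts Holstebro peaks above 24 and below 45 ng/L as primary events but requires no ischaemic classification for them, so the second analysis cannot be carried out as written without deciding how to treat them. As worded, that analysis also lacks a denominator. Ascertainment of infarction in that range may be incomplete; it is not shown to be.

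The size is unknown. About 1 to 14 of 59 planned injury events (2–24%) is an illustration that rests on the assumed Holstebro and between-threshold shares. Equal under-recording would cost absolute difference and power and leave the risk ratio unchanged. Unequal recording is possible but undemonstrated. The change should be made because it is cheap and settles the handling before unblinding. Confidence is medium.

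**What to change.** 1. **Classification rule.** In the protocol's Statistics section, for the statistical classification only, replace the 45 ng/L figure with the site's troponin threshold under Primary outcome. Every event counted as injury, and every patient meeting the troponin limb of infarction, is then classified by the same doctor's evaluation. That evaluation is made without knowledge of allocation, and from existing records where no bedside evaluation was done. Write the task into the protocol, because Allocation and blinding assigns it to nobody. Framing the rule by threshold, not by injury status, also captures infarctions identified by a falling troponin.
2. **Second analysis.** Define it as ischaemic myocardial injury (yes/no) by arm over the SAP's intention-to-treat population, not as a comparison restricted to ischaemic patients. State that non-ischaemic elevations count as no. Carry the definition into the SAP if the analysis is to be reported with the primary publication.
3. **Unclassifiable events.** Report them by arm. Analyse them both ways: as ischaemic and as not ischaemic, and likewise as infarction and as no infarction.
4. **Reconciliation.** The sponsor must reconcile Primary outcome and Secondary outcome (including the baseline footnote, which gives only 45 ng/L), Participant timeline and Statistics. No clinical threshold or ECG trigger is proposed here.

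The cost is a few sentences and a small record review at Holstebro: illustratively 1 to 14 injury patients, plus any who meet only the infarction limb. The downside is that some events may stay unclassifiable for lack of an ECG, so the two-way analysis may give a range and not a single figure.

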**The primary analysis**

Comparing the incidence of myocardial injury (No. (%)) in the intervention group versus the control group. We plan to use a chi-square test. The difference is considered to be significant if the two-sided p-value < 0.05.

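### The second, ischaemic-only analysis is defined by whom it includes, and its denominator is not stated; followed as written, it cannot compare incidence between the arms

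*Combined protocol and SAP*

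**What the plan says.** The Statistics section of the current protocol has two steps.

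- **Classification.** "A medical doctor will evaluate all patients with a rise in cTnI" to 45 ng/L or more, and the purpose is to "determine whether the elevation in cTnI is due to an ischemic or non-ischemic disease".
- **Analysis.** There will be "an analysis, which includes all patients (ischemic and non-ischemic"), followed by "a second analysis, which will only include patients with an ischemic disease". The older protocol in the same file plans the same pair.

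The Participant timeline schedules troponin "preoperative and in the morning at days 1, 2, 3 and 4 after surgery". The primary outcome is a count of patients whose peak troponin I reaches the threshold "during surgery or during the first 4 days after surgery (perioperative myocardial injury"). The threshold is 45 ng/L, or above 24 ng/L at Holstebro. A patient already elevated before surgery also needs a rise of at least 20%.

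The final SAP defines the primary analysis as "Comparing the incidence of myocardial injury (No. (%)) in the intervention group versus the control group", tested by chi-square. Its populations depend on randomisation, treatment received and at least two postoperative troponin values, not on the cause of an elevation. Neither the original nor the final SAP mentions an ischaemic-only analysis.

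**The concern.** The ischaemic or non-ischaemic label describes the cause of a troponin elevation. Patients without an elevation never receive it, and it rests mostly on samples taken after the intervention. An analysis that includes only patients with the ischaemic label therefore selects on something close to the primary outcome. It loses the patients without injury, who are needed to compute an incidence, and it loses the protection of randomisation.

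At stake is the one planned analysis that splits the primary endpoint by cause and could show whether fewer treated patients have ischaemic injury. The wording allows more than one analysis set, and the sets give different results. Neither document fixes the choice before the data are seen.

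**Working it through.** **Inputs from the documents.** Injury rates of 15% (control) and 7% (intervention), two-sided alpha 5%, power 80%, 264 per arm required and 270 per arm to be evaluated (SAP, Sample size). **Assumption.** A share f of injuries is judged ischaemic, equal in both arms. The documents give no figure, so a range is shown.

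**1. The plan's own figure.** With p̄ = 0.11 and d = 0.08:

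n = [1.960·√(2·0.11·0.89) + 0.842·√(0.15·0.85 + 0.07·0.93)]² / 0.08² = 239 per arm.

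With the continuity correction, n/4·[1 + √(1 + 4/(n·d))]² = 264 per arm. The plan's figure is reproduced, so its rates can be used for illustration.

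**2. Expected injuries.** 270 × 0.15 = 40.5 and 270 × 0.07 = 18.9, a risk ratio of 18.9/40.5 = 0.467.

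**3. Reading A: only patients labelled ischaemic are analysed.**

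- f = 0.3: 40.5 × 0.3 = 12.2 control and 18.9 × 0.3 = 5.7 intervention patients.
- f = 0.7: 40.5 × 0.7 = 28.4 and 18.9 × 0.7 = 13.2.

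Nearly all of these patients are cases, so incidence is close to 100% in both arms and the assumed risk ratio of 0.467 cannot appear. It is not exactly 100%. A patient at or above 45 ng/L before surgery without a 20% rise can be labelled without meeting the primary outcome.

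**4. Reading B: only patients with non-ischaemic injury are dropped.** At f = 0.5:

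- Control: 20.25 / (270 − 20.25) = 20.25/249.75 = 8.1%.
- Intervention: 9.45 / (270 − 9.45) = 9.45/260.55 = 3.6%.
- Risk ratio 0.447, against 0.467 with everyone kept.

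An extreme case shows the mechanism. Let ischaemic injury be 7.5% in both arms and non-ischaemic injury 7.5% versus 0%. The analysis then gives 0.075/(1 − 0.075) = 8.1% versus 7.5%, a difference produced by the exclusion alone.

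**5. Reading C: only ischaemic injuries count as events, and all 270 per arm stay in the denominator.** The risk ratio stays at 0.467. Power of the uncorrected chi-square test is Φ{[√n·(p₁ − p₂) − 1.960·√(2p̄(1 − p̄))] / √(p₁(1 − p₁) + p₂(1 − p₂))}. At f = 0.5 this is Φ{(0.657 − 0.632)/0.321} = 53.1%.

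| f | Control | Intervention | Power |
|---|---|---|---|
| 0.25 | 3.75% | 1.75% | 29.5% |
| 0.50 | 7.5% | 3.5% | 53.1% |
| 0.75 | 11.25% | 5.25% | 71.8% |
| 1.00 | 15.0% | 7.0% | 84.6% |

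**6. Who has a label.** The Participant timeline and Statistics sections start the evaluation at 45 ng/L. At Holstebro the event starts above 24 ng/L. Holstebro events above 24 and below 45 ng/L have no planned label under any reading. Their number cannot be derived from the documents.

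**The case against.** The strongest reply is that the sentence was never meant to define a denominator. The companion analysis is described as covering ischaemic and non-ischaemic patients, yet only patients with a rise carry either label. Taken as a denominator, that phrase would confine even the first analysis to patients with a rise, which contradicts the SAP's primary comparison. The word patients may therefore mean patients counted as injured, as in the primary outcome, which is itself a number of patients. The second analysis would then be reading C, which is valid. This is plausible, and I would not claim that the authors intended an invalid analysis. But the protocol speaks of including patients, not of redefining the event, and neither SAP version settles it.

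Four stronger inferences are tempting and are not supported:

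- *That this is the plan's only test of ischaemic events.* Perioperative myocardial infarction is a secondary outcome that in most of its pathways requires evidence of ischaemia. It stays in the final SAP as a comparison between arms.
- *That peak or area-under-the-curve troponin will be compared within the ischaemic subset.* No section plans this; the final SAP stratifies those outcomes by assay only.
- *That the primary result is compromised.* The primary chi-square test does not use the restriction.
- *That the restriction is a legitimate baseline subgroup.* The label concerns the cause of the elevation; it is not the eligibility criterion of ischaemic heart disease.

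It is also fair to say that the bias under reading B is small at the planned rates.

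**Conclusion.** The point holds as a fault of definition in a supporting analysis. As written, the second analysis would contain about 12–28 control and 6–13 intervention patients, nearly all of them cases, and could not compare incidence. These counts rest on the planned rates and on an assumed ischaemic share of 30–70%. Dropping only the non-ischaemic injuries moves the risk ratio from 0.467 to 0.447 at a 50% share, a small shift but one still made by excluding patients on their outcome. Only counting ischaemic injuries over the full analysis set gives a comparison of the arms as randomised, and no section states it. The correction is worth making before analysis because it decides what this analysis can conclude.

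**What to change.** **Protocol, Statistics.** Replace the sentence on the second analysis with: *The second analysis compares between arms the proportion of patients with ischaemic myocardial injury (primary-outcome definition met and elevation judged ischaemic). All patients of the main analysis set are in the denominator; patients with a non-ischaemic elevation are kept and counted as having no ischaemic injury.*

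**Final SAP, Secondary analyses.** List this endpoint among the secondary comparisons, so that protocol and SAP agree that it is planned.

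**Holstebro.** Reconcile the 45 ng/L evaluation trigger with the site's event threshold of above 24 ng/L. State how events there without a label are handled, for example by a sensitivity analysis that counts them first as ischaemic and then as non-ischaemic. They should not pass silently into the non-ischaemic group.

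**Cost.** One protocol sentence, one SAP line, one handling rule and a small amount of extra analysis. The labels are already planned, apart from the Holstebro gap. Power is lower than for all injury (about 53% against 84.6% at a 50% ischaemic share), so a non-significant result should not be read as evidence of no effect on ischaemic injury.
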